### 3.3.2 Safety Variables

Safety variables include:

- Incidence of treatment emergent adverse events (TEAEs), defined as an adverse event (AE) that is first identified, or is identified to worsen in intensity, at a time point occurring after the first dose of study drug
  - All TEAEs by System Organ Class (SOC) and Preferred Term (PT)
  - All TEAEs by PT
  - TEAEs by maximum severity (according to CTCAE version 4.03)
  - Treatment related TEAEs (TRAЕ) defined as events with a relationship to any study drug of ‘Definitely Related’, ‘Probably Related’ or ‘Possibly Related’
  - Treatment related TEAEs by maximum severity (according to CTCAE version 4.03)
  - TEAEs leading to study drug withdrawal
  - Serious TEAEs
- Change in clinical laboratory parameters (hematology, chemistry, amylase, lipase, thyroid) from baseline to each selected post-treatment assessment time point and shifts in clinical laboratory parameters from baseline to each selected post-treatment assessment time point
- Change in vital signs (systolic and diastolic blood pressure, heart rate, respiratory rate, and body temperature) from pre-dose to end of infusion at selected post-treatment assessment time points
- Change in ECOG performance status from baseline to last assessment
- Shifts in ECG from baseline to each selected post-treatment assessment time point

- Shifts in ECHO or MUGA from baseline to each selected post-treatment assessment time point

### **3.3.3 Immunological Response**

The following immunological response variables are being analyzed by another entity and are not included in the analysis sections below:

## **3.4 Subjects Disposition and Evaluability**

### **3.4.1 Subject Disposition**

Subject disposition will be presented by cohort and overall. The number of subjects enrolled and in the ITT and PP populations will be presented.

The following will be summarized:

- number and percentage of ITT subjects experiencing a DLT
- number and percentage of ITT subjects discontinuing study treatment and the reasons for treatment discontinuation
- number and percentage of ITT subjects completing and not completing the study (through 90 day on Study Follow-up period), and the reasons for study discontinuation
- number and percentage of ITT subjects entering and discontinuing from the Follow-up Extension, and the reasons for discontinuation

Descriptive statistics will also be presented for duration of time in study for subjects (start of therapy to last visit of follow-up).

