 - Grade \geq 3 neutropenia that (1) is not associated with fever or systemic infection, (2) does not require medical intervention, and (3) improves to Grade 2 within 7 days.
 - Grade 3 or Grade 4 lymphopenia.

- Grade 3 thrombocytopenia that (1) is not associated with clinically significant bleeding, (2) does not require medical intervention, and (3) improves to Grade 2 within 7 days.
- Isolated Grade 3 electrolyte abnormalities that are not associated with clinical signs or symptoms and are reversed with appropriate maximal medical intervention within 3 days.
- Any pre-existing laboratory abnormality that deteriorates to Grade 3/4, but where the increment of deterioration is considered not clinically significant by both Investigator and Sponsor.

Immune-related AEs (irAEs) are defined as AEs of immune nature (i.e., inflammatory) in the absence of a clear alternative etiology. In the absence of clinical abnormality, repeat laboratory testing will be conducted to confirm significant laboratory findings prior to designation as a DLT.

While rules for adjudicating DLTs are specified above, an AE that is Grade < 3 or listed as exempt above may also be defined as DLT after consultation with the Sponsor and Investigators, based on the emerging safety profiles of MEDI4736 and motolimod, and in combination with PLD. Likewise, subjects who become not evaluable for DLT, because they discontinued or interrupted treatment due to toxicities other than DLTs, may be counted as DLT subjects, if the toxicities cannot be managed in accordance with the dosing modifications described in Section 3.1.8.

Subjects who experience a DLT will be discontinued from study therapy and will enter the On Study Follow-up phase of the study (see Sections 3.1.16 and 3.2). However, if it is in the best interest of the subject, the Investigator and Sponsor may agree to continue treatment, possibly at a lower dose level.

The MTD of combination treatment is defined as the highest dose of MEDI4736 + motolimod + PLD studied, for which the observed incidence of DLT is less than 33% (based on n=6).

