3.1.11 Subject Evaluability and Replacements

Phase 1: Subjects are fully evaluable for DLT if they fulfill the criteria for the Per-Protocol Population for DLT Assessment as defined in Section 4.2.2.

Subjects who are not fully evaluable for DLT *will* be replaced.

Phase 2: Subjects are fully evaluable for the primary endpoint of clinical efficacy, if they fulfill the criteria for the Per-Protocol Population (as defined in Section 4.1.2). Subjects who are not fully evaluable per protocol *may* be replaced.

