4.2.2 Subject Evaluation & Statistics

The Per-Protocol (PP) Population for DLT Assessment includes:

- All subjects who experience a DLT at any time during the DLT Evaluation Period (as defined in Section 3.1.9)
- All subjects with no DLT who receive at least 75% of the scheduled doses of MEDI4736, motolimod (pre Amendment 2), and PLD as well as respective safety assessments, without major protocol violations, over the entire DLT Evaluation Period (as defined in Section 3.1.9).

Refer to Section 3.1.11 for subject replacements.

The Intent-To-Treat (ITT) Population for safety and tolerability is defined as all subjects who receive at least one dose of PLD, motolimod (pre Amendment 2) or MEDI4736.

In Phase 1, for the primary endpoint of determining DLTs and the MTD, the analysis of safety and tolerability will be based on the PP Population for DLT Assessment.

In both Phases 1 and 2, the overall analysis of safety and tolerability will be based on the ITT Population for safety and tolerability.

Appropriate summaries of AEs, laboratory data and vital sign data will be presented. Adverse events will be coded using the MedDRA dictionary. Incidences of treatment-emergent adverse events (TEAE, those events that started after dosing or worsened in severity after dosing) will be presented overall and by maximum severity (according to CTCAE version 4.03) and relationship to study medication.

For each continuous laboratory parameter, results will be categorized as low, normal, or high based on the laboratory normal ranges. Frequencies and percentages will be presented by treatment arm for the shifts in these categories (i.e., low to normal, low to high, high to low, etc.) from baseline to each post-treatment assessment time point. Additionally, for each continuous hematology and chemistry parameter, descriptive statistics will be presented by treatment arm for the changes from baseline to each post-treatment assessment time point. Descriptive statistics will be presented by cohort for the changes in vital signs from baseline to each post-treatment assessment time point.

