### **3.2.2 Per-Protocol Population**

The Per-Protocol (PP) Population is defined as all subjects enrolled in Phase 2 of the study, including the 6 subjects treated in Phase 1 at the MTD, who received at least 75% of the scheduled doses of MEDI4736 and PLD over the first 2 cycles, as well as respective disease assessments, without major protocol violations.

**Phase 2:** The Per-Protocol (PP) Population for Phase 2 is defined as all subjects enrolled in Phase 2 of the study who received at least 75% of the scheduled doses of MEDI4736 and PLD over the first 2 cycles, as well as respective disease assessments, without major protocol violations.

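### The SAP omits the protocol's DLT-evaluable population and tabulates DLTs, the Phase 1 primary endpoint, only on all treated subjects with no time window

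*SAP*

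**What the plan says.** The objectives table in Protocol 4 makes DLT/MTD the Phase 1 primary endpoint. Protocol 4.2.2 states that, for this endpoint, "the analysis of safety and tolerability will be based on the PP Population for DLT Assessment". That population has two parts. The first is "All subjects who experience a DLT at any time during the DLT Evaluation Period". The second is "All subjects with no DLT who receive at least 75% of the scheduled doses of MEDI4736" and of the other study drugs, with the corresponding safety assessments and no major violations, over the whole period. The same section keeps ITT for the overall safety analysis in both phases. Protocol 3.1.9 limits the period to Cycle 1 plus the pre-dose assessment for Cycle 2, and sets the MTD as the highest dose studied "for which the observed incidence of DLT is less than 33% (based on n=6"). Protocol 3.1.11 adds that "Subjects who are not fully evaluable for DLT" are to be replaced.

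The SAP has two populations. SAP 3.2.1 defines ITT as everyone who received at least one dose of any study drug. SAP 3.2.2 begins "The Per-Protocol (PP) Population is defined as all subjects enrolled in Phase 2 of the study", adds the six Phase 1 subjects at the MTD, and requires 75% of doses over two cycles with disease assessments.

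DLTs then appear in three places:
- SAP 3.4.1, in disposition, as the "number and percentage of ITT subjects experiencing a DLT".
- SAP 3.9.1.1, as one line of the adverse event overview (Table 14.3.1, ITT Population).
- SAP 3.9.1.6, which provides listings only.

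SAP 3.9 puts all safety analyses on ITT. DLT is not among the safety variables in SAP 3.3.2.

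**The concern.** A primary endpoint has no planned analysis on the population the protocol assigned to it. The SAP's per-protocol set cannot stand in. It is an efficacy set over two cycles, and it leaves out every Phase 1 dose level other than the MTD. The SAP says in its introduction that its methods follow Protocol Amendment 4 and restates the MTD objective in 2.1, but it neither mentions nor justifies the change of population.

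Two differences follow. Treated subjects who were not evaluable for DLT, and were replaced, enter the ITT denominator. DLTs after Cycle 1 can enter the ITT numerator, because neither summary line has a time window. Someone who sets the study report's only DLT percentage beside the protocol's MTD definition would be comparing different quantities. What is at stake is the faithful reporting of the Phase 1 primary endpoint.

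**Working it through.** **Inputs**
- MTD line: observed DLT incidence below 33%, n = 6 (Protocol 3.1.9).
- Protocol basis: in-period DLTs over DLT-evaluable subjects (Protocol 4.2.2).
- SAP basis: any DLT over all treated subjects (SAP 3.4.1, 3.9, 3.9.1.1).
- Non-evaluable Phase 1 subjects are replaced (Protocol 3.1.11), so a cohort's treated number can exceed its evaluable number.
- DLTs outside the period exist as a category and are also evaluated (Protocol 3.1.9).
- Not in the documents: m, the number of treated non-evaluable subjects in a cohort, and l, the number of subjects whose DLT came only after the period. I assume m from 0 to 4 and l from 0 to 2. I also assume that none of the m subjects is counted as a DLT, and that late-DLT subjects are among the six evaluable. The last assumption reads the second part of the protocol's population as meaning no DLT during the period.

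**Step 1: reproduce the plan's own line.** With x in-period DLTs the rate is x/6. 1/6 = 16.7% meets the definition, 2/6 = 33.3% does not, and 3/6 = 50.0% does not. The line therefore means at most 1 of 6.

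**Step 2: denominator effect, x/(6 + m), with no late DLTs.**

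| In-period DLTs | m = 0 | m = 1 | m = 2 | m = 3 | m = 4 |
|---|---|---|---|---|---|
| 1 | 16.7% | 14.3% | 12.5% | 11.1% | 10.0% |
| 2 | 33.3% | 28.6% | 25.0% | 22.2% | 20.0% |
| 3 | 50.0% | 42.9% | 37.5% | 33.3% | 30.0% |

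The ITT rate falls as m grows. With 2 DLTs, one extra subject moves it below 33%. With 3 it takes four. With 1 it never changes side.

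**Step 3: numerator effect, (1 + l)/(6 + m), with one in-period DLT.** The protocol rate is 1/6 = 16.7% throughout.
- l = 1: 2/6 = 33.3% at m = 0, 2/7 = 28.6% at m = 1, 2/8 = 25.0% at m = 2.
- l = 2: 3/6 = 50.0% at m = 0.

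Here the ITT rate is too high.

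**Step 4: neither effect.** With m = 0 and l = 0 the two rates are identical.

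**The case against.** A reader might infer that the SAP dilutes the rate on which the MTD was decided. The documents do not support that:
- No section compares the ITT percentage with 33%. It is a descriptive line in disposition and in the adverse event overview.
- The MTD definition is tied to n = 6, so 2/7 and 2/8 are not the quantity it uses.
- Escalation ran under 3+3 rules with documented safety reviews (Protocol 4.2) and replacement of non-evaluable subjects.
- SAP 2.2 describes escalation as done and Phase 2 enrolment as starting after the MTD was established.

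All of this stands. It limits the effect to reporting.

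Dilution as the single direction of error is not supported either. It needs at least one treated non-evaluable subject, and late DLTs push the other way. The 2-of-6 example was chosen because it sits at the line. Protocol 3.1.9 also narrows both effects: some subjects who become non-evaluable through unmanageable toxicity may be counted as DLTs, and late DLTs may inform dose decisions. An all-period count therefore has some protocol support as secondary information.

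Finally, the raw information is not lost. Disposition is shown by cohort, and there are listings of DLTs, drug administration and protocol deviations (16.2.20, 16.2.10, 16.2.2). ITT reporting is also consistent with the protocol's overall safety analysis.

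None of this supplies the missing analysis. A reader who had to rebuild the evaluable set from listings would be making, after the fact, choices that the protocol had already specified.

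**Conclusion.** The point holds as a conflict between SAP and protocol over the Phase 1 primary endpoint. If the SAP is followed as written, the study report contains no DLT rate on the protocol's population. The rate it does contain is on all treated subjects with no time window. That much is certain from the text.

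The size and direction of any misstatement are unknown, because the documents give neither the number of treated non-evaluable subjects nor the number of late DLTs. Under the assumed counts the gap runs from none, through 33.3% reported as 28.6% or 25.0%, to 16.7% reported as 33.3%. The declared MTD and the choice of Phase 2 dose level are not called into question. This should be corrected, as a matter of reporting.

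**What to change.** In SAP 3.2, define the DLT-evaluable population as in Protocol 4.2.2, and state that its no-DLT part refers to the DLT Evaluation Period. In SAP 3.9.1.6 and the list of tables, add one table by Phase 1 dose level showing DLTs during that period as n/N (%) on this population. Show non-evaluable or replaced subjects and late DLTs separately, so that the step from the evaluable to the treated number can be followed. Keep the ITT counts in SAP 3.4.1 and 3.9.1.1 and the DLT listing, labelled as supportive. The cost is a few lines of SAP wording and one small table, using data on dosing, assessments and DLTs that the trial already records.

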### **3.4.2 Protocol Deviations**

Protocol violations and deviations are recorded in a written log. Any major protocol deviations will be described in the study report.

## **3.5 Demographics and Baseline Characteristics**

### **3.5.1 Demographics**

Subject demographics, height and weight will be summarized for the ITT and PP populations.

Descriptive statistics will be provided for age (years), height (cm), and weight (kg). Frequencies and percentages will be tabulated for sex, race, ethnicity, disease staging at initial diagnosis and study entry, and for prior anti-cancer treatment use and the corresponding indications.

### **3.5.2 Medical History**

The number and percentage of subjects having a non-oncological medical condition in each body system will be summarized for the ITT Population. Non-oncological medical history will be presented in a subject listing.

### **3.5.3 Oncological Treatment History**

. Prior oncological treatment, radiation and surgical history will be presented in subject listings.

## **3.6 Prior and Concomitant Medications/Procedures**

Prior and concomitant medications will be coded using the World Health Organization (WHO) Drug dictionary (Version Dec 2014).

A concomitant medication is defined as any drug or substance administered between the time of the first dose of study treatment and the time of the last study visit. This includes medications that were started prior to screening, if their use continued during or after dosing. In order to define whether a medication with missing start or stop dates is a concomitant medication, refer to the following additional criteria.

- if both the start and stop dates of a particular medication are missing, that medication will be considered concomitant;
- if the start date of a medication is missing and the stop date of that medication falls on or after the first dose date, that medication will be considered concomitant;
- if the start date of a medication is missing and the stop date of the medication is prior to the first dose date, that medication is considered *not* concomitant;
- If the start date of a medication is prior to the first dose date and the stop date of the medication is missing, that medication is considered concomitant.

Concomitant medication use will be classified by Anatomical Therapeutic Class (ATC) level 4 and PT for the ITT population. For the presentation of concomitant medications, the ATC level 4 terms will be sorted alphabetically, and within ATC level 4 term, the PT will be used and presented by decreasing total frequency overall.

Frequencies and percentages of subjects using each concomitant medication will be presented for the ITT population. Prior and concomitant medications and concomitant procedures/surgeries will be presented in subject listings.

### **3.7 Treatment Exposure**

For each subject, treatment duration and the total number of cycles treated will be calculated based on the expected treatments for that subject in accordance with their assigned cohort. Treatment duration (weeks) will be calculated for each subject as:  $([\text{date of last dose of any study drug received} - \text{date of first dose of any study drug received} + 1] / 7)$ .

Descriptive statistics for treatment duration and the total number of treatment cycles will be displayed. The number of doses and cumulative dose received will be summarized for PLD, MEDI4736, and Motolimod. Study drug administration will be presented in a subject listing.

### **3.8 Efficacy Analysis**

#### **3.8.1 Progression-free Survival**

The primary endpoint in Phase 2 of this study is the PFS rate at 6 months defined as the visit at the start of Cycle 7, where progression is assessed for subjects based on a combination of RECIST v1.1 and/or the clinician's assessment of clinical progression or death. The primary efficacy analysis will be based on the Per Protocol population. A sensitivity analysis will be conducted on the ITT population. A secondary efficacy analysis will be conducted on the Phase 2 Per Protocol population.

The primary efficacy analysis entails testing the null hypothesis that PFS at 6 months is less than or equal to 25% against the alternative hypothesis that PFS at 6 months is higher for those treated with PLD and MEDI4736 combination. This hypothesis will be tested at  $\alpha=0.05$  using the 90% two-sided confidence interval for the PFS rate at 6 months based on Kaplan-Meier product limit estimates. The null hypothesis will be rejected in favor of the alternative if the lower bound of that confidence interval is greater than 25%. The null hypothesis will also be tested using a one-sided binomial test as a sensitivity analysis. In this analysis, if a subject has no tumor response assessment, or discontinued treatment or withdrew from the study for other reasons, he or she will be considered as "progressed." The null hypothesis will be rejected in favor of the alternative if the lower bound of a two-sided 90% binominal confidence interval is greater than 25%.

Table displays will include PFS rate at 6 months and the corresponding 90% confidence interval along with the corresponding number of subjects at risk. In addition, PFS will be presented graphically.

Secondary efficacy analyses will use the secondary efficacy endpoints listed in section 3.3.1 of the SAP and will be based on the ITT population. PFS rate and the corresponding 95% confidence interval will be calculated based on Kaplan-Meier product limit estimates and will be displayed by cohort and phase.

Descriptive analyses of PFS will include the following:

- Number and percentage of subjects that died or had a confirmed progression,
- Number and percentage of subjects that survived without a confirmed progression,
- Number and percentage of subjects lost to follow up (unknown survival and/or progression status), and
- Number of subjects missing the tumor response assessment

PFS time will be summarized for each cohort and phase and will include the 25th percentile, median, 75th percentile, corresponding 95% CIs, minimum and maximum, where PFS time will be calculated using the Kaplan-Meier method. In addition, PFS will be presented graphically.

PFS time is defined as time from the start date of the treatment (Day 1) to the first occurrence of confirmed progression (clinical or radiological), or the date of death due to any cause, whichever occurs first. Subjects without documentation of progression at the time of the analysis will be censored at the date of the last tumor response assessment, date of start of alternate therapy, or last contact if in post study follow-up, whichever comes first. Subjects with no tumor response assessment will be censored at the start date of the treatment.

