3.1.6 Sample Size and Statistical Considerations

Phase 1 of this trial will employ the 3+3 design as described in Section 3.1.7. The maximum tolerated dose (MTD) is defined as the highest dose for which fewer than 33% of subjects experience a dose-limiting toxicity (DLT).

Phase 2 of this trial will expand the Phase 1 cohort that was treated at the MTD. For the subject population to be enrolled, standard of care treatment with PLD alone has been reported to result in a 25% 6-months PFS rate. (47-50) A true 6-months PFS rate of $\geq 45\%$ in the current study, using motolimod + MEDI4736 with standard of care, would be of interest and represent a clinically meaningful improvement, while $\leq 25\%$ would be of no interest. Therefore, the study will test the hypotheses $H_0: p \leq 0.25$ versus $H_1: p \geq 0.45$, with p being the proportion of subjects who have survived and not progressed at 6 months, based on RECIST v1.1 criteria. Expansion of the Phase 1 MTD cohort to 41 evaluable subjects will yield 80% power to test the null hypothesis of 6-months PFS rate of $\leq 25\%$ against the alternative hypothesis of a PFS rate of $\geq 45\%$ at an alpha level of 0.05 (one-sided) based on exact test for single proportion.

PER Amendment 2, motolimod dosing will be discontinued for all subjects.

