3.1.10 Subject Withdrawal from Treatment or Study

A subject will be **withdrawn from study treatment** for any of the following reasons:

1. Withdrawal of consent for further treatment.
2. Pregnancy or intent to become pregnant.
3. Dose-limiting toxicity at any time (see Section 3.1.9 for definition of DLT and permitted continuation).
4. Confirmation of progressive disease by irRECIST criteria requiring alternative treatment.
5. Significant protocol violation or noncompliance that, in the opinion of the Investigator or Sponsor, warrants withdrawal.
6. Development of intercurrent, non-cancer related illnesses or complications that prevent either continuation of therapy or regular follow-up.
7. Best medical interest of the subject (at the discretion of the Investigator)

Discontinuation from receiving study treatment does not mean that the subject is withdrawn from the study. If feasible, subjects who are withdrawn from study treatment should enter the On Study Follow-Up, followed by the Post Study Follow-up (see Sections 3.1.16 and 3.2).

Subjects who begin other anti-cancer therapy should immediately be considered off-study and proceed to the Post Study Follow-up (see Section 3.1.16).

A subject will be **withdrawn from the study** for the following reasons:

1. Best medical interest of the subject at the discretion of the Investigator.
2. Initiation of alternative anti-cancer therapy including marketed or another investigational agent.
3. Withdrawal of consent for all follow-up.
4. Lost to follow-up.
5. Death

General subject withdrawal criteria are outlined in the Administrative, Legal and Ethical Requirements section of the protocol (see Section 7.2.6).

See also Sections 8.2, 8.3, and 8.4 for subject withdrawal from treatment due to necessary dosing interruptions or discontinuations.

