i - Standard of Care procedures may be used for eligibility assessments provided they meet the criteria specified in either the inclusion criteria or flowchart													

CONFIDENTIAL

Study Flowchart for All Subjects Except Dose Level 0a Cohort (Cont)	Treatment												On Study Follow-up			Post Study Follow-Up
	Cycle 7		Cycle 8		Cycle 9		Cycle 10		Cycle 11		Cycle 12		Last Study Drug Administration	Last Study Drug Administration	Last Study Drug Administration	
Cycle week	1		1		1		1		1		1		+28 ±3 days ^h	+56 ±7 days	+90 ±7 days End of Study	
Visit Day per Cycle	1±3	3±1	1±3	3±1	1±3	3±1	1±3	3±1	1±3	3±1	1±3	3±1				
Target Cumulative Visit Day	169	171	197	199	225	227	253	255	281	283	309	311				
Phase 1 & 2 STUDY DRUG ADMINISTRATION																
Pegylated liposomal doxorubicin - PLD (IV)	X		X		X		X		X		X					
MEDI4736 (IV)		X		X		X		X		X		X				
Tumor & Disease Assessments																
Disease Staging (date/stage at 1st diagnosis and at study entry)																
Disease Assessment by RECIST and irRECIST (including appropriate imaging)	X							X					+84 ± 7 days from last disease assessment			
Study Procedures & Examinations																
Eligibility Assessment and Informed Consent (IC) ⁱ																
Demographics (incl. DoB; sex; race; ethnicity)																
Medical history																
Physical Exam (incl. weight and ECOG Perf Status)	X		X		X		X		X		X		X	X	X	
Height																
Vital Signs (T, HR, BP, RR) ^b	X	X	X	X	X	X	X	X	X	X	X	X	X	X	X	
12-Lead ECG ^a	X		X		X		X		X		X		X		X	
Echocardiogram or MUGA						X							X			
Concomitant Medication / Procedure (name, indication, dose, route, start & end dates)	X	X	X	X	X	X	X	X	X	X	X	X	X	X	X	
Adverse Events (starting or worsening after IC) ^d	X	X	X	X	X	X	X	X	X	X	X	X	X	X	X	
Specimens for Laboratory Procedures																
Blood Hematology (complete blood count, differential, platelets) ^a	X	X	X	X	X	X	X	X	X	X	X	X	X	X	X	
Chemistry (gluc., BUN, crea., Na, K, Ca, Cl, CO2, PO4, Mg, prot., alb., Tbili., AST, ALT, ALP, LDH) ^a	X	X	X	X	X	X	X	X	X	X	X	X	X	X	X	
Chemistry cont. (Amylase and lipase) ^a	X	X	X	X	X	X	X	X	X	X	X	X	X	X	X	
Chemistry cont. (Free T3, Free T4, TSH) ^a	X		X		X		X		X		X		X	X	X	
Serum pregnancy test ^{a,f}	X				X				X				X		X	
CA-125 ^a	X		X		X		X		X		X		X			
Urine Pregnancy Test ^{a,f}																
Specimens for Correlative Assessments																
PBMC/Plasma Collection & Banking ^{a,g}	X												X		X	
MDSC (Seramatrix) ^{a,g} (US sites only)	X												X			

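### The binomial sensitivity test of 6-month PFS scores every subject who stopped treatment or withdrew for other reasons as progressed, with no time limit and no exception for a progression-free Cycle 7 scan.

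*SAP*

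**What the plan says.** SAP 3.8.1 makes the Kaplan-Meier estimate of 6-month PFS the primary test and adds a one-sided binomial test as a sensitivity analysis. For the binomial test, a subject is scored as progressed when no tumour assessment exists. The rule then adds two further conditions: "discontinued treatment or withdrew from the study for other reasons, he or she will be considered as". The status assigned is again progression. The conditions are alternatives, so any one of them suffices.

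The protocol defines the tested quantity without reference to treatment status (Protocol 3.1.6): "with p being the proportion of subjects who have survived and not progressed at 6 months, based on RECIST v1.1 criteria". Protocol 4.1.1.1 and SAP 2.2.3.1 take status from the disease assessment at the start of Cycle 7, target Day 169.

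Stopping treatment does not end observation. Protocol 3.1.10 states: "Discontinuation from receiving study treatment does not mean that the subject is withdrawn from the study". The flowchart in Protocol 3.2 schedules the follow-up scan at "84 ± 7 days from last disease assessment", and Protocol 3.1.16 sets On Study Follow-up at 90 days after the last study drug. Core treatment can run for up to 12 months (Protocol 3.1.15), well past the 6-month visit.

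**The concern.** The rule mixes two kinds of subject. For those whose 6-month status is unknown, scoring them as failures is an ordinary conservative choice. For those whose status is known and favourable, the rule replaces an observation with its opposite. Two groups fall in the second class:

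- subjects with a progression-free Cycle 7 assessment who stop treatment or withdraw at any later time;
- subjects who stop in about Cycles 4 to 6 and still have the Day 169 scan during follow-up.

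This matters because the binomial test is the only form in which the SAP keeps the test that sized the trial. Protocol 3.1.6 set the sample size "at an alpha level of 0.05 (one-sided) based on exact test for single proportion", and Protocol 4.1.2 based the decision on a binomial confidence limit. If the binomial and Kaplan-Meier results disagree, a reader cannot tell whether the cause is missing data or the recoding of known non-progressors.

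**Working it through.** **Inputs.** Null rate 25%, alternative 45%, one-sided alpha 0.05, exact test, 41 evaluable subjects, 80% power (Protocol 3.1.6). Pass rule: lower bound of the two-sided 90% binomial interval above 25% (SAP 3.8.1). I use the Clopper-Pearson interval, since the planned test is exact. The share *d* of truly progression-free subjects who are recoded is not in the documents; I assume 5% to 20%.

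**1. The plan's own figure.** The smallest *r* with P(X ≥ *r* | n = 41, p = 0.25) ≤ 0.05 is 16. The exact alpha is 0.0333, and power = P(X ≥ 16 | n = 41, p = 0.45) = 0.8225. The stated sample size and 80% power are confirmed.

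**2. Who has a Day 169 scan after stopping.** A Day 85 scan plus 84 days gives Day 169. A last dose on Cycle 4 Day 3 (Day 87) gives follow-up to 87 + 90 = Day 177, which covers it. A last dose on Cycle 3 Day 3 (Day 59) gives 59 + 90 = Day 149, which does not. The break-even last dose is 169 − 90 = Day 79.

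**3. Effect per subject.** Recoding one subject lowers the rate by 1/41 = 2.4 points. The lower limit for *x* successes is the 5th percentile of Beta(*x*, 41 − *x* + 1):

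| Progression-free | Rate | Lower limit | Result |
|---|---|---|---|
| 18/41 | 43.9% | 30.6% | pass |
| 16/41 | 39.0% | 26.2% | pass |
| 15/41 | 36.6% | 24.1% | fail |

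At 16/41, one recoded subject reverses the result; at 18/41, three do.

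**4. Effect on the chance of passing.** Scored rate = 0.45 × (1 − *d*). Chance of passing = P(X ≥ 16 | n = 41, scored rate). The last column uses 0.25 × (1 − *d*).

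| Assumed *d* | Scored rate | Chance of passing | False-positive rate at a true 25% |
|---|---|---|---|
| 0 | 45.0% | 82.3% | 0.033 |
| 5% | 42.8% | 73.7% | 0.021 |
| 10% | 40.5% | 63.4% | 0.013 |
| 15% | 38.3% | 51.8% | 0.007 |
| 20% | 36.0% | 40% | 0.004 |

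These losses are upper bounds on what a corrected rule would recover. The assumed share can include subjects with no Day 169 scan, who would still be scored as progressed.

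**5. The SAP's practice elsewhere.** For ORR and disease control, SAP 3.8.2 treats dropouts as non-responders only if they leave before meeting the response criteria. Section 3.8.1 has no matching limit.

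**The case against.** The strongest reply is that this is a sensitivity analysis and is meant to be harsh. The Kaplan-Meier primary censors subjects without documented progression, which assumes that censoring is uninformative. Counting every discontinuation as a failure is a recognised stress test of that assumption. It cannot create a false positive, and it leaves the primary decision alone. All of this stands, and it limits the weight of the point. It does not justify overriding an observed scan, because the assumption under test concerns unknown status.

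A second reply is that 3.8.1 opens by tying the endpoint to the Cycle 7 visit, so a 6-month cut-off was probably intended. That may be so, but it is not written. It would also leave unsettled the subjects who stop before that visit and are scanned at it.

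Several stronger readings are tempting, and the documents do not support them:

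- *The trial's primary result or power is compromised.* The pass probabilities above belong to the sensitivity test only.
- *Everyone who stops early has a usable scan.* Protocol 3.1.10 asks for follow-up only where feasible and takes subjects who start other anti-cancer therapy off study. Stops in the first three cycles generally end follow-up before Day 169.
- *Stopping for hand-foot syndrome triggers the rule.* Under Protocol 3.1.8, MEDI4736 may continue after PLD is stopped for PLD toxicity, provided at least two PLD doses were given. Such a subject need not have discontinued treatment. The SAP does not say whether stopping PLD alone counts.
- *The 25% benchmark counted toxicity stops differently.* The protocol says only that "standard of care treatment with PLD alone has been reported to result in a 25% 6-months PFS rate" and does not describe how the cited studies handled stops.

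**Conclusion.** The point holds as a defect of wording in one conservative secondary test. As written, the rule scores some known non-progressors as progressed at 6 months, contrary to the endpoint definition. The direction is certain: the scored rate is at or below the observed rate. The size is not known, and with no such subjects there is no effect. It could still change the outcome of this test, since one subject is enough at the threshold. The fall from 82% to between 74% and 40% rests on an assumed recoding share of 5% to 20%, a true rate of 45% and an analysed sample of 41. A reader might infer that the reported 6-month PFS rate will be understated in general. That does not follow, because the primary estimate does not use this rule.

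**What to change.** Replace the rule in SAP 3.8.1 with wording such as:

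> In this analysis, 6-month status is taken from the Cycle 7 (Day 169) disease assessment. A subject is scored as progressed if no evaluable assessment establishes progression-free status at that time point, or if alternate anti-cancer therapy was started before it. Stopping treatment or withdrawing after that assessment does not change 6-month status. Stopping treatment before it does not override a progression-free Cycle 7 assessment obtained without alternate therapy.

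The alternate-therapy clause is needed. Without it, a stable scan obtained on another cancer drug would count as a success, whereas the Kaplan-Meier rules in SAP 3.8.1 censor at the start of such therapy.

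If the version in which all discontinuations fail is kept, label it as supplementary and state whether stopping PLD alone counts as discontinuing treatment.

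The cost is a short SAP edit and a programming change. The scans are already scheduled. The one downside is that the sensitivity analysis becomes somewhat less conservative.
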